6.3.4 TREATMENT PROCEDURES

6.3.4.1 Visit 2 (First Operative Day 0)

- 1) Assess demographics, medical and surgical history, current ocular and systemic conditions, prescription medications, and medications known or suspected to lower IOP.
- 2) Assess any adverse events.
- 3) Prepare subject for surgery.

CLINICAL PROTOCOL

Date: September 18, 2019	Protocol No.: IDOS-402-IVIV
-----------------------------	--------------------------------

- 4) Administer an additional drop of antibiotic 30 minutes preoperatively.
- 5) Visually confirm Shaffer grade angle and target implant location.
- 6) Obtain a treatment kit.
- 7) Administer anesthetic (topical, general, retrobulbar, peribulbar).
- 8) Perform surgery.
- 9) Record clinical data from the surgical procedure on the First Operative Day 0 CRF, noting study eye intra-operative AEs and post-operative AEs.

Postoperatively:

- 10) Schedule the subject to return for Visit 3 (Day 1).
- 11) Dispense other postoperative medications and instruct the subject as follows:
[REDACTED]

[REDACTED]

[REDACTED]

[REDACTED]

6.3.4.2 Visit 3 (Day 1 Exam, 1 days postoperative)

- 1) Update subject's medical status and concomitant medications.
- 2) Assess study eye adverse events.
- 3) Measure pinhole visual acuity (Snellen).
- 4) Perform slit-lamp biomicroscopy.
- 5) Measure IOP (can be measured at any time) and record the time (observer).
- 6) Schedule the subject to return for Visit 4 (Day 10).

6.3.4.3 Visit 4 (Day 10 Exam, 10 ± 3 days postoperative)

- 1) Update subject's medical status and concomitant medications.
- 2) Assess study eye adverse events.
- 3) Measure pinhole visual acuity (Snellen).
- 4) Perform slit-lamp biomicroscopy.
- 5) Measure IOP (can be measured at any time) and record the time (observer).

CLINICAL PROTOCOL

Date:

September 18, 2019

Protocol No.:

IDOS-402-IVIV

- 6) Schedule the subject to return for Visit 5 (Week 4).

6.3.4.4 Visit 5 (Week 4 Exam, 28 days ± 3 postoperative)

- 1) Update subject's medical status and concomitant medications.
- 2) Assess study eye adverse events.
- 3) Measure corrected visual acuity (ETDRS). A manifest refraction and best spectacle corrected visual acuity (ETDRS) should be performed if corrected VA (ETDRS) has decreased by 2 or more lines (≥ 10 letters) from Visit 1 (Screening).
- 4) Perform slit-lamp biomicroscopy.
- 5) Measure IOP (can be measured at any time) and record the time (observer).
- 6) Perform a gonioscopic examination.
- 7) Schedule the subject to return for the next visit(s) if applicable (see next section)

6.3.4.5 Depending on the cohort, the subject may have one or more of the following visits (please see APPENDIX A-G: SCHEDULE OF VISITS & MEASUREMENTS):

Visit 5.1, (Month 6, 182 days ± 14)

Visit 5.2, (Month 12, 365 days ± 14)

Visit 5.3, (Month 18, 547 days ± 14)

- 1) Update subject's medical status and concomitant medications.
- 2) Assess study eye adverse events.
- 3) Measure corrected visual acuity (ETDRS). A manifest refraction and best spectacle corrected visual acuity (ETDRS) should be performed if corrected VA (ETDRS) has decreased by 2 or more lines (≥ 10 letters) from Visit 1 (Screening).
- 4) Perform slit-lamp biomicroscopy.
- 5) Measure IOP (can be measured at any time) and record the time (observer).
- 6) Perform a gonioscopic examination.
- 7) Schedule the subject to return for Visit 6 (Pre-Exchange Exam). Remind the subject of the following:

i. Visit 6 (Pre-Exchange Exam) is the visit prior to the Second Operative Visit

ii.

CLINICAL PROTOCOL

Date:
September 18, 2019

Protocol No.:
IDOS-402-IVIV

6.3.4.6 Visit 6 (Pre-exchange Exam), to occur within 10 days prior to Visit 7 (Second Operative / Exchange Exam)

- 1) Update subject's medical status and concomitant medications.
- 2) Assess study eye adverse events.
- 3) Measure corrected visual acuity (ETDRS). A manifest refraction and best spectacle corrected visual acuity (ETDRS) should be performed if corrected VA (ETDRS) has decreased by 2 or more lines (≥ 10 letters) from Visit 1 (Screening).
- 4) Perform slit-lamp biomicroscopy.
- 5) Measure IOP (can be measured at any time) and record the time (observer).
- 6) Perform a gonioscopic examination.
- 7) Schedule the subject to return for Visit 7. Remind the subject of the following:

- i. Visit 7 is the Second Operative / Exchange Visit*
- ii.*

6.3.4.7 Visit 7 (Second Operative / Exchange Exam)

Depending on the cohort, the subject may have their Visit 7 (Second Operative / Exchange Exam) occur on one of the following visits (please see **APPENDIX A-G: SCHEDULE OF VISITS & MEASUREMENTS):**

CLINICAL PROTOCOL

Date:
September 18, 2019

Protocol No.:
IDOS-402-IVIV

(Month 12, 365 days ± 14)

(Month 3, 91 days ± 14)

(Month 6, 182 days ± 14)

(Month 24, 730 days ± 14)

(Month 21, 637 days ± 14)

(Month 18, 547 days ± 14)

(Month 15, 456 days ± 14)

- 1) Update subject's medical status and concomitant medications.
- 2) Assess study eye adverse events.
- 3) Prepare subject for surgery.
- 4) [REDACTED]

The following steps will be performed in the Operating Room:

- 5) Visually confirm Shaffer grade angle and target implant location.
- 6) Collect an anterior chamber aqueous humor sample (AC tap).
Please follow instructions in the procedure manual.

After collecting the AC Tap and performing all assessments:

- 7) Obtain a treatment kit.
- 8) Administer anesthetic [REDACTED]
- 9) Perform second surgery (Exchange).
- 10) Collect the first implant for shipment back to sponsor.
- 11) Record clinical data from the surgical procedure on the Second Operative CRF, noting study eye intra-operative AEs and post-operative AEs.
- 12) Schedule the subject to return for Visit 8 (Day 1 Post Exchange).

6.3.4.8 Visit 8 (Day 1 Post-Exchange Exam)

- 1) Update subject's medical status and concomitant medications.
- 2) Assess study eye adverse events.
- 3) Measure pinhole visual acuity (Snellen).
- 4) Perform slit-lamp biomicroscopy
- 5) Measure IOP (can be measured at any time) and record the time (observer).
- 6) Schedule the subject to return for Visit 9 (Day 10 Post - Exchange).

CLINICAL PROTOCOL

Date: September 18, 2019	Protocol No.: IDOS-402-IVIV
-----------------------------	--------------------------------

6.3.4.9 Visit 9 (Day 10 Post -Exchange Exam, 10 days ± 3)

- 1) Update subject's medical status and concomitant medications.
- 2) Assess study eye adverse events.
- 3) Measure pinhole visual acuity (Snellen).
- 4) Perform slit-lamp biomicroscopy
- 5) Measure IOP (can be measured at any time) and record the time (observer).
- 6) Schedule the subject to return for Visit 10 (Week 4 Post-Exchange)

6.3.4.10 Visit 10 (Week 4 Post-Exchange Exam, 28 days ± 3)

- 1) Update subject's medical status and concomitant medications.
- 2) Assess study eye adverse events.
- 3) Measure corrected visual acuity (ETDRS). A manifest refraction and best spectacle corrected visual acuity (ETDRS) should be performed if corrected VA (ETDRS) has decreased by 2 or more lines (≥ 10 letters) from Visit 1 (Screening).
- 4) Perform slit-lamp biomicroscopy
- 5) Measure IOP (can be measured at any time) and record the time (observer).
- 6) Perform a gonioscopic examination.

6.4 Concomitant Therapies

6.4.1 MEDICATIONS OR TREATMENTS

Therapy considered necessary for the subject's welfare that will not interfere with the evaluation of the study medication may be given at the discretion of the investigator.

6.4.2 USE OF CONTACT LENSES

Contact lens wear is allowed in this study. Subjects are to be instructed to remove their contact lenses in the study eye prior to instillation of study medications and to wait for 20 minutes before inserting their contact lenses after instillation of medication.

CLINICAL PROTOCOL

Date: September 18, 2019	Protocol No.: IDOS-402-IVIV
-----------------------------	--------------------------------

7 EXTENT OF EXPOSURE AND TREATMENT COMPLIANCE

All subjects will be implanted with a Travoprost Intraocular Implant. All subjects will then be implanted with a second Travoprost Intraocular Implant (at either month 12, 3, 6, 24, 21, 18, or 15, depending on cohort assignment) to exchange with the first one that will be explanted. All subjects will be followed for 4 weeks following the exchange procedure for a total duration of 4 to 25 months.

8 STATISTICAL ANALYSES

One database lock is planned after all subjects have exited from the study. Prior to the database lock, a Statistical Analysis Plan (SAP) will be approved.

8.1 Sample Size

The sample size of 210 subjects who undergo implantation and exchange of a Travoprost Intraocular Implant was determined empirically. This sample size is considered adequate to provide information on the safety of the exchange procedure.

8.2 Analysis Populations

All subjects contributing aqueous humor samples and/or exchanged implants will be included in the correlation model development and analysis population. All subjects who receive an implant will be included in the safety population. The safety population will be used for all data tabulations and listings.

8.3 General Statistical Methods

All demographic and safety data collected will be displayed in data listings. No formal statistical testing will be performed.

Continuous measures will be summarized with descriptive statistics including the number of observations, mean, standard deviation, median, minimum, and maximum. Summary statistics for categorical measures include the percentage and number of cases. All data tabulations will be by cohort as well as overall.

8.4 Efficacy Analyses

There are no efficacy measures in this study. IOP is evaluated for safety.

CLINICAL PROTOCOL

Date:
September 18, 2019

Protocol No.:
IDOS-402-IVIV

8.5 Safety Analyses

8.5.1 ADVERSE EVENTS

Adverse events (AEs) in the study eye will be coded using the Medical Dictionary for Regulatory Activities (MedDRA) nomenclature. Treatment Emergent Adverse Events (TEAE) are defined as those AEs that occur after the initial treatment at Visit 2 (Operative Day 0).

AEs that occur on the date of the procedure are classified as either intra-operative or post-operative. Post-operative AEs are considered to be TEAEs. Intra-operative AEs and TEAEs will be summarized separately.

A line listing of serious adverse events will be provided.

8.5.2 OTHER SAFETY MEASURES

Details of analyses for other safety measures (see Section 4.2) will be provided in the SAP.

8.6 Other

[REDACTED] derived from the
explant analyses and aqueous humor drug concentration levels will be
summarized.

8.7 Interim Analyses

No interim analyses are planned.

9 ADVERSE EVENTS

An Adverse Event (AE) is defined as any untoward and unintended medical occurrence (e.g., sign, symptom, disease, syndrome) that occurs in a study subject, regardless of the suspected cause during the study. Adverse events will be clearly documented on the study source document and monitored throughout the course of the study.

Events occurring after signing the informed consent but prior to the implant procedure should be documented in the medical history. Events observed during or after the initial implant or exchange procedure until the final study visit, are to be recorded as AEs if they are in the study eye and deemed related to the implant or procedure.

CLINICAL PROTOCOL

Date:
September 18, 2019

Protocol No.:
IDOS-402-IVIV

Any clinically significant change in a subject's condition after receiving the study treatments, regardless of causality, is to be considered an adverse event, unless the change is determined to be a continuation of a pre-existing condition that is documented in the subject's medical history. If an adverse event occurs, an AE form must be completed.

An AE includes any of the following:

- An exacerbation or an unexpected increase in frequency or intensity of a pre-existing condition, including intermittent or episodic conditions
- New conditions or illnesses detected or diagnosed after the implant procedure
- A suspected interaction with any of the study treatments
- Signs, symptoms, or the clinical sequelae of a suspected overdose of either any of the study treatments or a concomitant medication
- Any clinically significant laboratory finding that was not present prior to receiving any of the study treatments

An AE does NOT include any of the following:

- Anticipated day-to-day fluctuations of any pre-existing conditions, including the disease under study (OAG and OHT).
- Medical or surgical procedure, (e.g., colonoscopy or hernia repair). The condition that led to the procedure may be an AE, if not present in medical history.
- Hospitalizations where an untoward medical occurrence did not occur (social or convenience admission to the hospital).
- Pre-existing conditions or diseases that were present before receiving any of the study treatments that do not worsen or that are chronic but stable
- Changes in a chronic condition or disease that are consistent with natural disease progression. (These medical conditions should be adequately documented).
- Lack of efficacy of the study treatment for the condition being investigated.

AEs will be graded on a 3-point scale and reported in detail as indicated on the CRF:

Mild: easily tolerated, causing minimal discomfort and not interfering with normal everyday activities

Moderate: sufficiently discomforting to interfere with normal everyday activities

Severe: incapacitating and/or preventing normal everyday activities

CLINICAL PROTOCOL

Date:
September 18, 2019

Protocol No.:
IDOS-402-IVIV

The relationship of each AE to study treatment should be determined by the investigator using the following explanations:

Definitely Unrelated: the event is clearly related to other factors such as the subject's clinical state, therapeutic interventions, or concomitant medications administered to the subject

Unlikely Related: the event is most likely produced by other factors such as the subject's clinical state, therapeutic interventions, or concomitant medications administered to the subject; and does not follow a known response pattern to the study medication

Possibly Related: the event follows a reasonable temporal sequence from the time of drug administration; and/or follows a known response pattern to the study medication; but could have been produced by other factors such as the subject's clinical state, therapeutic interventions, or concomitant medications administered to the subject

Probably Related: the event follows a reasonable temporal sequence from the time of drug administration; and/or follows a known response pattern to the study medication; and is not likely to have been produced by other factors such as the subject's clinical state, therapeutic interventions, or concomitant medications administered to the subject

Definitely Related: the event follows a reasonable temporal sequence from the time of drug administration; and follows a known response pattern to the study medication; and cannot be reasonably explained by other factors such as the subject's clinical state, therapeutic interventions, or concomitant medications administered to the subject

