1 INTRODUCTION

Glaucoma is a group of eye diseases characterized by progressive, irreversible and largely asymptomatic vision loss caused by optic nerve damage, which is most commonly associated with elevated levels of intraocular pressure.

Glaucoma is a chronic condition that progresses slowly over long periods of time and can have a devastating impact on a patient's vision and quality of life. Reducing intraocular pressure currently is the only proven treatment for glaucoma.

[figure not shown]
Treatment for open-angle glaucoma (OAG) traditionally has started with topical ocular hypotensive medical therapy. Development of more effective medications has increased the popularity of this approach as initial treatment compared to more invasive incisional or drainage device surgery.

Furthermore, the more benign medication treatments preserve the ocular tissues in the event that more invasive surgical approaches are eventually required.

The various topical ocular medications available to reduce IOP include miotics, β -adrenergic receptor antagonists (β -blockers), carbonic anhydrase inhibitors (CAIs), α -adrenergic receptor agonists (α -agonists), and prostaglandin analogues (PGs). The PGs are a class of ocular hypotensive agents that have been proven effective in lowering IOP in subjects with OAG or OHT. Other advantages of this class of medications is that the systemic side effects associated with α -agonists (e.g., dry mouth, drowsiness) and β -blockers (e.g., depression, fatigue, bradycardia) do not appear to be associated with PGs. Furthermore, the ocular side effects typically associated with α -agonists (e.g., allergic reactions), and cholinergic agents (e.g., reduced vision), do not seem to manifest with the use of PGs.

However, PGs have been shown to be associated with side effects such as ocular hyperemia, iris hyperchromia, periorbital atrophy, increased eyelash growth, general ocular surface discomfort and headache.¹⁻⁵ These side effects and other factors including cost, compliance, and the difficulty of proper instillation, can sometimes hinder the proper use of topical medications.^{6,7} Some patients may possess or develop an intolerance to topical medications or the preservatives in their formulations.

The Travoprost Intraocular Implant was developed to remove or minimize the issue of patient compliance with topical hypotensive medication. This clinical protocol

CLINICAL PROTOCOL

Date:
September 18, 2019

Protocol No.:
IDOS-402-IVIV

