4 STUDY MEASURES

4.1 Efficacy

There are no efficacy measures in this study. IOP is assessed for safety.

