6.3.3 PREOPERATIVE PROCEDURES

6.3.3.1 Visit 1 (Screening)

- 1) Written informed consent.
- 2) Assign subject number.
- 3) Demographics, medical and surgical history, current ocular and systemic conditions, prescription medications, and medications known or suspected to lower IOP.
- 4) A pregnancy test (if applicable) may be administered at any time during this visit.

CLINICAL PROTOCOL

Date:
September 18, 2019

Protocol No.:
IDOS-402-IVIV

- 5) Measure best spectacle corrected visual acuity through manifest refraction (ETDRS) in each eye.
- 6) Perform slit-lamp biomicroscopy (including crystalline lens).
- 7) Measure IOP (can be measured at any time) and record the time.
- 8) Pachymetry.
- 9) Perform a gonioscopic examination.
- 10) Perform a dilated ophthalmoscopy/fundus examination.
- 11) Assess optic nerve abnormality (ophthalmoscopy).
- 12) Assess vertical C/D ratio.
- 13) Review screening inclusion and exclusion criteria. Do not continue screening any subject who does not meet the screening eligibility requirements.

If the subject is qualified:

- 1) Schedule the subject for Visit 2 (First Operative Day 0).
- 2) [REDACTED]
- 3) Advise the subject to discontinue taking their topical hypotensive medication beginning the morning of visit 2 (First Operative Day)
[REDACTED]

If the subject is ineligible for the study, complete the appropriate CRF.

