9.1 Serious Adverse Event

Serious adverse events are defined as any findings that suggest a significant hazard, contraindication, side effect, or precaution. Any adverse event is considered a serious adverse event if it results in any of the following outcomes:

- Death
- Life- or sight-threatening
- Overnight hospitalization or prolongation of an existing hospitalization
- A persistent or significant disability/incapacity
- A congenital anomaly/birth defect

CLINICAL PROTOCOL

Date: September 18, 2019	Protocol No.: IDOS-402-IVIV
-----------------------------	--------------------------------

The terms “mild,” “moderate,” and “severe” are measures of intensity; thus a severe AE is not necessarily serious. For example, nausea of several hours duration may be rated as severe but may not be clinically serious.

Important medical events that may not result in death, be life-threatening, or require overnight hospitalization may be considered a serious adverse drug experience when, based upon appropriate medical judgment, they may jeopardize the subject and may require medical or surgical intervention to prevent one of the outcomes listed above. A life-threatening event is any event that places the subject at substantial risk of death from the event as it occurred; it does not refer to an event that hypothetically might have caused death if it were more severe. A sight-threatening event is any event that places the subject at risk of permanently losing vision in either eye as a direct result of the event.

Serious adverse events must be reported to Glaukos immediately (preferably within 24 hours of knowledge of the event).

When new significant information (including the outcome of the event) is obtained, the investigator should inform Glaukos as soon as possible. Depending on the nature of the AE, Glaukos may request copies of the ophthalmic and medical records of the subject. If the subject was hospitalized for a study-treatment related serious adverse event, a copy of the discharge summary must be forwarded to Glaukos as soon as possible.

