7.1.3.8. Intraocular Pressure

IOP is assessed for safety and is measured at Screening and all postoperative visits within each study period (Day 1, Day 10, Week 4, Month 6, Month 12, Month 18, Pre-Exchange, Day 1 PE, Day 10 PE, and Week 4 PE). IOP measurements will be taken once daily, unless surgery is performed. At each visit, IOP may be collected at any time of the day.

The actual and CFB in IOP (mmHg) will be summarized by visit [REDACTED]. The number and percentage of subjects will also be tabulated by visit [REDACTED] for the following categories:

- IOP ≥ 30 mmHg
- IOP Increase ≥ 10 mmHg

For visits belonging to the PE study period, the CFPE will also be summarized both continuously and categorically as outlined.

A subject listing presenting all IOP data will be provided.

8. Other Analyses

Other analyses will be summarized as outlined in the subsequent sections.

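### The adverse-event definition excludes lack of efficacy although IOP is a safety-only variable, and no rule says whether a clinically significant IOP rise is recorded

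*Protocol*

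**What the plan says.** Protocol 4.1 states: "There are no efficacy measures in this study. IOP is assessed for safety". Protocol 8.4 and the synopsis repeat this. SAP 7.1.3.8 agrees: "IOP is assessed for safety and is measured at Screening and all postoperative visits within each study period". It counts subjects by visit in two categories, IOP of at least 30 mmHg and "IOP Increase ≥ 10 mmHg", and lists all IOP data.

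Protocol 9 gives a list of what an adverse event does not include. One entry is "Lack of efficacy of the study treatment for the condition being investigated". The entry has no exception for IOP or for events with a serious outcome.

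Subjects may enter on zero to three topical pressure-lowering drugs (Protocol 6.2.1.1). At screening the site is told: "Advise the subject to discontinue taking their topical hypotensive medication beginning the morning of visit 2". They then carry the first implant for 3 to 24 months, depending on cohort.

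Protocol 9.1 asks for serious adverse events to reach the sponsor immediately, with 24 hours as a preference. Sections 8 and 8.7 plan one database lock and no interim analysis.

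**The concern.** An exclusion for lack of efficacy normally keeps efficacy outcomes from being counted twice, once as efficacy and once as harm. Here there is no efficacy outcome to protect. The exclusion can only act on a variable that the protocol has assigned to safety.

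Loss of pressure control is a foreseeable hazard when drops are stopped and the eye depends on a drug reservoir for up to two years. If two assessors, or one assessor at two times, may classify the same rise differently, the adverse-event tables in SAP 7.1.2 cannot be read as a consistent count of IOP-increase events. The sponsor may also not be told promptly of a rise that threatens sight.

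**Working it through.** No statistical figure is at stake. The sample size of 210 (14 cohorts × 15 = 210, in the data analysis plan, section 2.3) is not power-based. The check sets the passages side by side.

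**Step 1. Does lack of efficacy reach IOP?** Protocol 1 says: "Reducing intraocular pressure currently is the only proven treatment for glaucoma". In this population, failure of the treatment is failure to lower IOP. The exclusion therefore covers uncontrolled or rising IOP.

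**Step 2. What else in Protocol 9 bears on an IOP rise?**

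| Text that would take the rise in | Text that would keep it out |
|---|---|
| A clinically significant change after treatment counts, whatever its cause | That same sentence exempts a continuation of a documented pre-existing condition, and every subject enters with OAG or OHT |
| An exacerbation of a pre-existing condition counts | Changes that fit the expected course of a chronic disease do not count |
| Pre-existing conditions are exempt only if they are stable or do not worsen | Lack of efficacy does not count |
| | After surgery, only study-eye events judged related to the implant or procedure are to be recorded |

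The relatedness filter in the last row also conflicts with the statement that cause does not matter. It conflicts as well with the five-level causality scale later in section 9, which includes an unrelated grade. A site that sees a late rise as the underlying disease re-emerging could use the filter on its own to leave the event unrecorded.

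**Step 3. Is there an order of precedence?** None is given. The exclusion permits non-recording; it does not require it.

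**Step 4. Does the gap carry into serious-event reporting?** Section 9.1 applies its outcome list, including sight-threatening events, to any adverse event. A rise already screened out may never be assessed against that list. The opening sentence of 9.1 is broader and speaks of findings that suggest a hazard, but it does not say that it overrides the exclusions in section 9.

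**Step 5. Do the IOP tables close the gap?** Partly. SAP 4 restricts tabulations to scheduled visits unless stated otherwise, and SAP 7.1.3.8 states nothing else. Nominal IOP days before exchange, after Week 4, come from Protocol 6.3.4 and Appendices A to G. The pre-exchange visit falls 0 to 10 days before exchange.

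- Group 3: 91 − 28 = 63 days, or 53 if the pre-exchange visit is 10 days earlier.
- Group 6: 182 − 28 = 154 days, or 144.
- Group 12: 365 − 182 = 183 days, or 173.
- Groups 15, 18, 21 and 24: the longest gap is 365 − 182 = 183 days, because Months 6 and 12 are both scheduled visits.

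A rise found at an unscheduled visit within such a gap and classed as lack of efficacy would enter no adverse-event table and no IOP table, only the IOP listing. Visual acuity, slit-lamp and lens findings are handled differently: SAP 7.1.3.1 to 7.1.3.3 bring unscheduled visits into a period summary.

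**The case against.** The strongest reply is that section 9, read as a whole, already captures a marked rise. The sentences on clinically significant change and on exacerbation are broad, and calling IOP a safety variable favours treating a rise as a safety event. This stands to the extent that a careful site could record every such rise. It does not settle the matter, because the exclusions and the relatedness filter are equally explicit.

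Four stronger readings are tempting, and the documents do not support them.

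- A reader might infer that adverse-event reporting is the sponsor's only sight of IOP during the trial. Electronic data capture with source verification (Protocol 15.2), record inspection by monitors (15.4) and submission of case report forms while the study is running (Appendix H) are further routes. They are slower than event-triggered reporting.
- A reader might infer that the IOP-increase rate is biased downward. That follows only if sites use the exclusion, and the IOP tables at scheduled visits do not depend on adverse-event coding.
- A reader might want a number of affected subjects. Table 1 is redacted and no event rate is given, so any count would rest wholly on assumption.
- A reader might infer that the implant is exhausted within follow-up. No visible text gives an exhaustion time, and Protocol 1 reports long-term pressure lowering in an earlier trial.

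Parts of the medication instructions are redacted, so nothing is concluded here about how raised IOP is managed.

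**Conclusion.** The conflict is real and lies in the current text. Protocol 9 excludes lack of efficacy from adverse events in a study where the only variable that can show it is declared a safety measure, and the surrounding text points both ways with no rule of precedence. A clinically significant IOP rise on the first implant may therefore go unrecorded as an adverse event and, through the wording of 9.1, unreported as a serious one.

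The effect is limited to adverse-event recording and prompt reporting. SAP 7.1.3.8 still counts large values and large increases at scheduled visits. The gap is widest between scheduled visits, which are up to 183 nominal days apart in the groups of 12 months or longer. The wording applies to all of the approximately 210 subjects; how many would be affected cannot be estimated from the documents. The conclusion rests on one inference, that lack of efficacy in OAG or OHT appears as raised IOP. It does not assume that the implant runs out before exchange.

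**What to change.** Reconcile Protocol 9 and 9.1 in one of two ways.

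- Delete the lack-of-efficacy exclusion. The disease-progression exclusion and the relatedness filter would then still need to be reconciled with the statement that cause does not matter.
- Or keep it and state that this exclusion, the disease-progression exclusion and the relatedness filter do not remove a clinically significant worsening of study-eye IOP from baseline from adverse-event recording.

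In either case, add that any event meeting a seriousness outcome is reported as serious whatever its attribution.

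Leave any IOP threshold to the sponsor and the investigator. A reader might want to turn the SAP's 30 mmHg category into an automatic adverse-event trigger. The entry criteria show no upper limit on IOP, so a subject at or above 30 mmHg at screening and unchanged afterwards would then be recorded as having an event, against section 9's own rule on conditions that do not worsen.

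In SAP 7.1.3.8, add a count by study period of the two existing categories that includes unscheduled visits, as is done for visual acuity, slit-lamp and lens findings.

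The cost is a short protocol clarification, a note to the site and one more table, with no new visit or measurement. The downside is more adverse-event forms and a higher reported rate of IOP-increase events.
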